10.9 Vital Signs

Vital signs (systolic and diastolic blood pressure, pulse rate, and respiratory rate) will be measured at the Screening Visit, on Admission (Day -1), Day 1 to Day 3 (Discharge) or as early termination assessments, as applicable. All parameters will be recorded in supine position after the subject has rested for at least 5 minutes. Subjects should have abstained from using any nicotine/tobacco containing products for at least 15 minutes prior to Vital signs assessment.

The Investigator will define vital sign ranges to determine normal or abnormal results. For those results outside of the normal range, the Investigator will determine appropriate follow up including reporting of any AEs.

Descriptive statistics will be reported for vital signs measurements (blood pressure, pulse, respiration, and temperature) by period. Change from baseline will be summarized in a similar manner. Baseline is defined as the result closest and prior to the first product administration, which may include unscheduled or recheck results. This will typically be the result collected on prior to T_0 on Day 1. Post product use unscheduled events or rechecks will not be included in summaries. Similarly, early termination results will not be included in summaries.

10.10 Electrocardiogram

An ECG will be recorded at Screening, Admission (Day -1), and at Day 3 or at early termination. The ECG testing will be performed as per the investigational site standard practice. A standard 12-lead ECG will be recorded after the subject has rested for at least 10 minutes in supine position.

The following parameters will be documented: heart rate, PR interval, QRS interval, QT interval, and QTc interval, corrected by the ECG device according to Fridericia's formula [QTcF]. Every ECG has to be assessed as normal, abnormal – not clinically significant, or abnormal – clinically significant.

Descriptive statistics will be presented for each ECG parameter by period. Change from baseline will be summarized in a similar manner. Baseline is defined as the result closest and prior to the first product administration, which may include unscheduled or recheck results. This will typically be the result collected at Admission (Day -1). Post product use unscheduled events or rechecks will not be included in summaries. Similarly, early termination results will not be included in summaries.

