7.4.6 Spirometry

Spirometry without bronchodilator will be performed at the Screening Visit, Day -1 and at Discharge (Day 3) or early termination in accordance with the 2005 guideline of the American Thoracic Society (ATS)/European Respiratory Society (ERS) Joint Task Force on the standardization of spirometry [23, 24]. Spirometry predicted values will be standardized to the National Health and Nutrition Examination Survey III predicted set [25].

Assessed parameters will include: FEV₁, FEV₁ % predicted, FVC, FVC % predicted and FEV₁/FVC.

All personnel performing spirometry testing should have the appropriate training and quality control measures should be put into place and be properly documented. The testing will be performed in sitting position at rest for at least 15 minutes and at least 1 hour after smoking cigarettes (Screening Visit).

The Investigator will define Spirometry ranges to determine normal or abnormal results. For those results outside of the normal range, the Investigator will determine appropriate follow-up including reporting of any AEs.

Confidentiality Statement

Data and information contained in this document are considered to constitute trade secrets and confidential commercial information, and the legal protections provided to such trade secrets and confidential information are hereby claimed under the provisions of applicable law. No part of this document may be publicly disclosed without the written consent of Philip Morris Products S.A.

Any printouts of Spirometry on thermo-sensitive paper must be photocopied and stapled together for inclusion in the source documents.

7.4.7 **Electrocardiogram**

At the Screening Visit, Day -1 and at Discharge (Day 3) or early termination, a standard 12-lead ECG will be recorded after the subject has rested for at least 10 minutes in supine position as described in the Schedule of events.

All ECGs will be reviewed on an ongoing basis by the Investigator or designee. The following parameters will be documented: heart rate, PR interval, QRS interval, QT interval, and QTc interval corrected according to Fridericia's formula.

The Investigator will define ECG ranges to determine normal or abnormal results. For those results outside of the normal range, the Investigator will determine appropriate follow-up including reporting of any AEs.

Any printouts of ECGs on thermo-sensitive paper must be photocopied and stapled together for inclusion in the source documents.

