12.1.3 Descriptive Statistics

All data will be presented in listings, ordered by subject, study visit, product, and time point, unless otherwise specified.

Continuous endpoints will be summarized with descriptive statistics including number of subjects (n), number and percent of subjects with missing data, arithmetic means and standard deviations (mean and SD), median, first and third quartiles, minimum and maximum.

For log normally distributed endpoints, geometric mean, geometric CV, and confidence interval will be presented additionally.

Nominal categorical variables will be summarized by frequency statistics (number and percentage), including the number of missing data as a category.

Ordinal categorical data (e.g., T_{max}) will be summarized by number of subjects (n), number and percent of subjects with missing data, median, first and third quartiles, and minimum and maximum.

For PK and PD endpoints, all analyses and summaries will be performed by product.

Confidentiality Statement

Data and information contained in this document are considered to constitute trade secrets and confidential commercial information, and the legal protections provided to such trade secrets and confidential information are hereby claimed under the provisions of applicable law. No part of this document may be publicly disclosed without the written consent of Philip Morris Products S.A.

For safety endpoints, analyses and summaries will be performed by product and sequence, and overall.

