12.6.6 Safety Endpoints

In general, all safety data will be listed and tabulated using the approach described in section [12.1.3](#). Safety variables collected during exposure periods will also be reported by sequence.

AE data will serve for the assessment of safety. Other safety variables monitored in this study include: incidence of P4M3 Gen 2.0 product events including malfunction/misuse; vital signs (systolic and diastolic blood pressure, pulse rate, respiratory rate); spirometry; ECG data; clinical chemistry, hematology, and urine analysis safety panel; physical examination; concomitant medication.

The number and percentage of subjects with AEs, SAEs, and product events will be tabulated by system organ class and preferred term. Summaries will also be presented for AEs leading to discontinuation, AEs leading to death, AEs by relatedness to product exposure, AEs by severity, and laboratory AEs. Tabulations will be performed for both the number of subjects experiencing an event and the number of events.

Safety laboratory assessments are performed on Day -1 and Day 3 in the morning prior to product use ([Appendix A](#)). Any lab related AEs on Day 3 will be assigned to the product used on the previous day.

Summary tables showing actual values and change from baseline of clinical findings will be provided for spirometry, ECGs, vital signs, and laboratory parameter. Descriptive statistics will be summarized by period for ECG and vital signs and by Day for laboratory parameters, ECG and vital signs.

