Data and information contained in this document are considered to constitute trade secrets and confidential commercial information, and the legal protections provided to such trade secrets and confidential information are hereby claimed under the provisions of applicable law. No part of this document may be publicly disclosed without the written consent of Philip Morris Products S.A.

- f. At Screening an ECG will be performed after signed ICF and at least 1 hour after smoking cigarettes, on Day -1 an ECG will be performed prior to enrollment, on Day 3 an ECG will be performed 60 minutes \pm 10 minutes after T₀.
- g. Blood samples should be taken in the morning of the Screening visit, Admission (Day -1) and Discharge (Day 3) or at Early termination. Subjects should have fasted for at least 10 hours prior to safety laboratory assessments except at the Screening visit and Early termination where non-fasting samples will be used.
- h. Tests for hepatitis B (HbsAg), hepatitis C (HCV antibody) virus and human immunodeficiency virus (anti-HIV1/2) will be performed at the Screening Visit.
- i. Sample taken prior to P4M3 Gen 2.0 product test.
- j. On Day -1, after enrollment, subjects will perform a product test using P4M3 Gen 2.0 Classic Auburn 3.5% variant (CA35) *ad libitum* for up to 10 minutes.
- k. On Day 1 to Day 3, subjects will smoke a single cigarette or will use one P4M3 Gen 2.0 with CA35 and CM35 variant *ad libitum* for 6 minutes (\pm 30 seconds) according to the randomized product use sequence. P4M3 Gen 2.0 use with the MDEDR puffing topography device connected with data recording for 6 minutes (\pm 30 seconds).

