Subject Number	Study Period	Was Assessment Completed?	Reason for Not Done	Date	Question*						Total Score	Classification of Nicotine Dependence
					1	2	3	4	5	6		
X	XXXX	XXX		DDMMYYYY	XXXX	XXXX	XXXX	XXXX	XXXX	XXXX	X	XXXXXXXXXX

Note: * 1 = How soon after you wake up do you smoke your first cigarette?

2 = Do you find it difficult to refrain from smoking in places where it is prohibited?

3 = Which cigarette would you hate most to give up?

4 = How many cigarettes per day do you smoke?

5 = Do you smoke more frequently during the first hours after awakening than during the rest of the day?

6 = Do you smoke even if you are so sick that you are in bed most of the day?

Program: /CAXXXX/sas_prg/stsas/lis_PROGRAMNAME.sas DDMMYYYY HH:MM Status: DRAFT (Page X of Y)

Philip Morris Products S.A.
P4M3 Gen 2.0, P4-PK-04-US

████████ Statistical Analysis Plan Number CA34617

Listing 15.3.1.10 Subject Discontinuation (Safety Population)

Subject Number	Product Sequence	Date of Last Contact	Did the Subject Complete the Study?	If No, Reason for Discontinuation	Specify	Primary Adverse Event Term
X	X	DDMMYYYY	XXX			
X	X	DDMMYYYY	XXX	XXXXXX		

Sequence 1: CA35-Cigarettes-CM35

Sequence 2: CA35-CM35-Cigarettes

Sequence 3: Cigarettes-CA35-CM35

Sequence 4: Cigarettes-CM35-CA35

Sequence 5: CM35-Cigarettes-CA35

Sequence 6: CM35-CA35-Cigarettes

CA35 = P4M3 Gen 2.0 Classic Auburn

CM35 = P4M3 Gen 2.0 Classic Menthol

Program: /CAXXXX/sas_prg/stsas/is_PROGRAMNAME.sas DDMMYYYY HH:MM- Status: DRAFT (Page X of Y)

Philip Morris Products S.A.
P4M3 Gen 2.0, P4-PK-04-US

████████ Statistical Analysis Plan Number CA34617

Listing 15.3.1.11 Protocol Deviations (Safety Population)

Subject Number	Product Sequence	Date	Deviation	Code Term	Major/ Minor	Deviation Category
X	X	DDMMYYYY	XXXXXXXXXXXXXXXXXXXX	XXXX	XXXXX	XXXXXXX

Sequence 1: CA35-Cigarettes-CM35
 Sequence 2: CA35-CM35-Cigarettes
 Sequence 3: Cigarettes-CA35-CM35
 Sequence 4: Cigarettes-CM35-CA35
 Sequence 5: CM35-Cigarettes-CA35

Sequence 6: CM35-CA35-Cigarettes CA35 = P4M3 Gen 2.0 Classic Auburn

CM35 = P4M3 Gen 2.0 Classic Menthol

Program: /CAXXXXX\sas_prg\stsas\ls_PROGRAMNAME.sas DDMMYYYY HH:MM Status: DRAFT (Page X of Y)

Philip Morris Products S.A.
P4M3 Gen 2.0, P4-PK-04-US

████████ Statistical Analysis Plan Number CA34617

Listing 15.3.2.1 Product Demonstration (Safety Population)

Subject Number	Study Period	Was a Product Demonstration Given?	If No, Reason For Not Done	Date
X	XXXX	XXX		DDMMYYYY

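### The planned ECG table averages the only ECG after randomised product use over CA35, CM35 and cigarettes; the protocol's product and sequence breakdowns are dropped without being declared.

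*SAP*

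**What the plan says.** The protocol gives three instructions that bear on ECG summaries.

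- Protocol 12.1.3, on safety endpoints: "For safety endpoints, analyses and summaries will be performed by product and sequence, and overall".
- Protocol 12.6.6 opens by pointing back to that rule: "In general, all safety data will be listed and tabulated using the approach described in section" 12.1.3. It then adds: "Safety variables collected during exposure periods will also be reported by sequence".
- The same section later says: "Descriptive statistics will be summarized by period for ECG and vital signs and by Day for laboratory parameters, ECG and vital signs".

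SAP 10.10 keeps only part of the last one: "Descriptive statistics will be presented for each ECG parameter by period". The shell for Table 15.2.3.4.1 has four data columns: values at Screening, Day -1 and Day 3, and change from baseline at Day 3. It has no product or sequence dimension. ECG Listings 15.3.4.5.1 and 15.3.4.5.2 carry neither product nor sequence, whereas the vital-sign listings have a study product column.

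Protocol 7.4.7 sets the schedule: "At the Screening Visit, Day -1 and at Discharge (Day 3) or early termination, a standard 12-lead ECG will be recorded". Appendix A, footnote f, fixes the last of these after product use: "on Day 3 an ECG will be performed 60 minutes" after T0, within 10 minutes either way.

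SAP Section 11 declares two changes from the protocol: the randomised population is dropped, and a CA35 versus CM35 comparison is added. It says nothing about how safety data are broken down.

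**The concern.** Change in ECG from baseline (heart rate, PR, QRS, QT, QTcF) is a named endpoint of secondary objective 4, and Protocol 2.1.2 says the product has not been tested in humans before. Protocol 2.3.3 lists increased heart rate among the foreseeable nicotine effects. The planned table would give one mean that mixes two test variants with their comparator, so a reader could not see the mean ECG change after any one product.

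There is also a question of documentation. The SAP drops breakdowns that the protocol asks for, and the section meant to list such departures is silent.

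**Working it through.** **Inputs**

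- 36 subjects randomised to 6 sequences (SAP 3.1). Equal allocation is assumed: 36/6 = 6 per sequence.
- Sequences from SAP 14.5, Listing 15.3.1.10, beginning "Sequence 1: CA35-Cigarettes-CM35".
- One ECG after randomised use, on Day 3 (Protocol 7.4.7, Appendix A, SAP 10.10). Early-termination ECGs are left out of the summaries (SAP 10.10).
- The documents give no ECG effect size or SD, so effects are written as *d* and precision is in SD units.

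**Step 1: which sequences use which product in each period**

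| Period | CA35 | CM35 | Cigarettes |
|---|---|---|---|
| 1 | 1, 2 | 5, 6 | 3, 4 |
| 2 | 3, 6 | 2, 4 | 1, 5 |
| 3 | 4, 5 | 1, 3 | 2, 6 |

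Every cell holds two sequences, so 2 × 6 = 12 subjects per product in each period. A by-period mean therefore pools the three products equally, whichever period is looked at. With one ECG after randomised use, by period and by Day also give the same single column.

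**Step 2: what the pooled mean shows**

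Pooled mean = (d_CA + d_CM + d_Cig)/3.

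- Effect *d* in one product only: 12d/36 = d/3.
- Effect *d* in both P4M3 variants only: 24d/36 = 2d/3.
- Equal effects in all three: d, with nothing lost.

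For example, a shift of 9 units confined to one product would appear as 3.

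**Step 3: precision if the table is split**

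The 95% CI half-width for one group is t(0.975, n−1)/√n. For a difference between two groups of size n it is t(0.975, 2n−2) × √(2/n).

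| Summary | 36 evaluable | 30 evaluable (assumed) |
|---|---|---|
| Pooled | 2.030/√36 = 0.34 | n = 30: 0.37 |
| One product | 2.201/√12 = 0.64 | n = 10: 0.72 |
| Difference, two products | 2.074 × √(2/12) = 0.85 | 0.94 |
| One sequence | 2.571/√6 = 1.05 | n = 5: 1.24 |

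**Step 4: whether the period/Day sentence replaces the others**

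Protocol 12.6.6 does not say that it does. The sequence sentence sits in the same section and is worded as an addition. Protocol 6.2.2 places Day 3 in the exposure period, so the Day 3 ECG falls under it. Protocol 12.1.3 is itself a rule for safety endpoints, not only a general rule for all data.

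**The case against.** The strongest reply is that the period/Day sentence names ECG and should govern over a rule that applies only in general. On that reading SAP 10.10 follows the protocol, and Section 11 has nothing to declare about product. This is arguable for product. It does not cover sequence, which is required in the same section and is missing from both SAP 10.10 and Section 11.

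Second, ECG is not singled out. Laboratory data (SAP 10.8), vital signs (10.9) and spirometry (10.13) are also summarised without product, although adverse events (10.7) and concomitant medication (10.11) are given by product. That is true, and changing ECG alone leaves the safety tables uneven. ECG still has the best claim to a split because its Day 3 recording has a stated post-use window. Vital signs on Days 1 to 3 are scheduled before T0, and Protocol 12.6.6 puts the Day 3 laboratory sample before product use.

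Third, a Day 3 split is weak evidence. It is between-subject, follows two earlier products and the CA35 product test, and is measured from a Day -1 baseline. This stands: with a half-width of 0.85 SD for a product difference, only large differences would show.

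Fourth, some attribution already exists. Clinically significant ECG findings become adverse events (Protocol 8.4.2), which are tabulated by product, and the ECG listings can be linked to the randomisation listing. SAP 14 also allows shells to change. All of this is correct, but mean ECG change by product would still be absent, and the SAP 10.10 text has the same gap as the shell.

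Finally, SAP Table 3 (4.2.1.3) lists ECG windows on Days 1, 2 and 3 and on a Day 4, which conflicts with the other schedules. Those passages must be reconciled. The point does not depend on the outcome, since Step 1 shows that any by-period mean pools the products.

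**Conclusion.** The concern holds, as a minor one. SAP 10.10 and Table 15.2.3.4.1 reduce the only ECG after randomised use to one mean over both test variants and the comparator. The sequence breakdown is omitted without being declared under any reading of the protocol. The product breakdown is omitted unless the period/Day sentence is taken to override Protocol 12.1.3, which the protocol does not say.

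The loss ranges from nothing, if the three effects are equal, to two thirds of an effect confined to one product. This rests on equal allocation, no dropout and a single Day 3 ECG. Safety-population subjects who had only the product test contribute no Day 3 ECG.

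No main result changes, and objective 4 does not ask for a product comparison.

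**What to change.** 1. In SAP 10.10 and Table 15.2.3.4.1, split the Day 3 value and the Day 3 change from baseline by the product used on Day 3, and keep the overall columns. Label the split as descriptive, between-subject, after two earlier products and the CA35 product test, and measured from the Day -1 baseline.
2. Either report ECG by sequence, or state in SAP Section 11 that this table is dropped and why. Each Day 3 product group is two sequences: CM35 is 1 and 3, cigarettes 2 and 6, CA35 4 and 5.
3. Add study product and sequence columns to Listings 15.3.4.5.1 and 15.3.4.5.2.
4. State in Section 11 how Protocol 12.1.3 and 12.6.6 are reconciled for ECG.
5. Separately, reconcile the ECG rows of SAP Table 3 with SAP 10.10, Protocol 7.4.7 and Appendix A. No ECG row is visible in Protocol Table 10, but the available text of that table is broken, so check it against the original.

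The cost is six extra columns in one table (3 for value, 3 for change, so 4 become 10), two columns in each of two listings, and one by-sequence table or one sentence. No new data are needed. The drawback is low precision: about 12 subjects per product and about 6 per sequence.

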10.11 Prior and Concomitant Medications

All prior and concomitant medications will be listed by subject and product using Anatomical Therapeutic and Chemical (ATC) codes (World Health Organization Drug Dictionary) Version

Philip Morris Products S.A.
P4M3 Gen 2.0, P4-PK-04-US
[REDACTED] Statistical Analysis Plan Number CA34617

01 Mar 2021. Concomitant procedures recorded during the study will be listed by subject. Concomitant medications will be summarized using frequency count by product.

10.12 Physical Examination

A physical examination will be conducted at the Screening Visit, at Admission (Day -1) and at the Day of Discharge (Day 3) or at early termination. All data found in the CRF will be listed. Physical examination has to be assessed as normal, abnormal – clinically not significant, or abnormal – clinically significant. Change in physical examination from baseline will be discussed in the clinical study report.

10.13 Spirometry

Spirometry without bronchodilator will be performed at the Screening Visit, Day -1, and at Discharge (Day 3) or early termination in accordance with the 2019 guideline update of the American Thoracic Society (ATS)/European Respiratory Society (ERS) Joint Task Force on the standardization of spirometry (Graham, B.L., et al., 2019). Spirometry predicted values will be standardized to the National Health and Nutrition Examination Survey III predicted set.

Assessed parameters will include: FEV1, FEV1% predicted, FVC, FVC% predicted, and FEV1/FVC.

Every Spirometry has to be assessed as normal, abnormal – clinically not significant, or abnormal – clinically significant.

Descriptive statistics will be presented for each spirometry parameter by study day. Change from baseline will be summarized in a similar manner. Baseline is defined as the result closest and prior to the first product administration, which may include unscheduled or recheck results. This will typically be the result collected at day -1. Post product use unscheduled events or rechecks will not be included in summaries. Similarly, early termination results will not be included in summaries.

10.14 Cytochrome P450 2A6 (CYP2A6) Activity

CYP2A6 activity drives the metabolism of nicotine to cotinine and subsequent metabolites. CYP2A6 activity will be measured in plasma using the metabolic molar ratio of trans-3'-hydroxycotinine/cotinine.

On Day -1, one blood sample will be collected for determination of CYP2A6 activity (cotinine and trans-3'-hydroxy-cotinine) prior to the P4M3 Gen 2.0 product test.

Individual results will be listed and descriptive statistics will be presented for the Safety population.

11. SUMMARY OF CHANGES FROM PROTOCOL-PLANNED ANALYSIS

Per protocol, demographics, baseline characteristics, pharmacokinetics endpoints, pharmacodynamics endpoints, human puffing topography parameters, amount of nicotine

Philip Morris Products S.A.
P4M3 Gen 2.0, P4-PK-04-US

██████████ Statistical Analysis Plan Number CA34617

delivered, will be analyzed using the randomized and PK population. They will be analyzed only in the PK population. The randomized population will not be defined.

Where comparisons between CA35 and Cigarettes, and between CM35 and Cigarettes, are performed, the comparison between CA35 and CM35 will be performed additionally.

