6.4 Blinding

This is an open-label study. Therefore, the subjects, the Investigator, the PMP and CRO personnel will be unblinded to the subject's sequence and product use.

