12.3 Analysis Populations

Populations will be described on the screened population.

Demographics, baseline characteristics, pharmacokinetics endpoints, pharmacodynamics endpoints, human puffing topography parameters, amount of nicotine delivered, will be analyzed using the randomized and PK population.

Safety will be analyzed using the safety population.

Confidentiality Statement

Data and information contained in this document are considered to constitute trade secrets and confidential commercial information, and the legal protections provided to such trade secrets and confidential information are hereby claimed under the provisions of applicable law. No part of this document may be publicly disclosed without the written consent of Philip Morris Products S.A.

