4.2.1.1 Major Protocol Deviations

Subjects with major protocol deviations will be identified (at a population level) to determine whether they will be excluded from any of the analysis populations.

Major deviations will include but are not limited to the deviations presented in [Table 1](#).

Table 1 - Definition of Major Protocol Deviation Categories

Sub-Category	Description
Violation	Violation of inclusion/exclusion criteria
Mis-randomization	Violation of the product allocation process, including but not limited to the misclassification of subject's sex at randomization and incorrect product administered according to randomized sequence
Mis-use of product	Use of any nicotine or tobacco-containing product other than the assigned product during the exposure period, or use of any nicotine tobacco-containing product during at least 10 hours of abstinence from any nicotine/tobacco containing products (nicotine wash-out). Product use not compliant with planned regimen
Concomitant medications	Use of any drugs which are known to affect CYP2A6 activity

Among the eligibility criteria, violations of inclusion criteria 1, 2, 3, 4 and 7, or of the exclusion criteria 2 and 15 will be considered as impacting the evaluability or integrity of the primary objective. Other major protocol deviations will be assessed for their impact on the evaluability of the primary objective during the pre-analysis data review meeting.

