15.3.3 Listings of PK Data

15.3.3.1 Plasma Nicotine Concentration and Pharmacokinetics Parameters

Listing 15.3.3.1.1 Listing of Individual Observed Plasma Nicotine Concentrations Versus Time of P4M3 Gen 2.0 CA35 (PK Population)

Listing 15.3.3.1.2 Listing of Individual Observed Plasma Nicotine Concentrations Versus Time of P4M3 Gen 2.0 CM35 (PK Population)

Listing 15.3.3.1.3 Listing of Individual Observed Plasma Nicotine Concentrations Versus Time of Cigarettes (PK Population)

Listing 15.3.3.1.4 Listing of Individual Background-Corrected Plasma Nicotine Concentrations Versus Time of P4M3 Gen 2.0 CA35 (PK Population)

Listing 15.3.3.1.5 Listing of Individual Background-Corrected Plasma Nicotine Concentrations Versus Time of P4M3 Gen 2.0 CM35 (PK Population)

Listing 15.3.3.1.6 Listing of Individual Background-Corrected Plasma Nicotine Concentrations Versus Time of Cigarettes (PK Population)

Listing 15.3.3.1.7 Individual Background-Corrected Plasma Nicotine PK Parameters of P4M3 Gen 2.0 CA35 (PK Population)

Listing 15.3.3.1.8 Individual Background-Corrected Plasma Nicotine PK Parameters of P4M3 Gen 2.0 CM35 (PK Population)

Listing 15.3.3.1.9 Individual Background-Corrected Plasma Nicotine PK Parameters of Cigarettes (PK Population)

Listing 15.3.3.1.10 Individual λz -related Plasma Nicotine PK Parameters Following P4M3 Gen 2.0 and Cigarettes (Day 2) (PK Population)

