15.3.5 Pharmacodynamic Effects and Human Puffing Topography

15.3.5.1 Subjective Measurement

Listing 15.3.5.1.1 Original Responses of ABOUT - Product Experience Questionnaire (PK Population)

Listing 15.3.5.1.2 Subscales of ABOUT - Product Experience Questionnaire (PK Population)

Listing 15.3.5.1.3 VAS Craving Assessment (PK Population)

Listing 15.3.5.1.4 VAS Liking Assessment (PK Population)

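### The SAP drops the randomized-population analyses that the protocol planned, so no planned analysis shows whether exclusions from the PK population change the results

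*SAP*

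**What the plan says.** The protocol commits to two analysis sets. Section 12.3 lists demographics, PK, pharmacodynamic and puffing endpoints and ends: "amount of nicotine delivered, will be analyzed using the randomized and PK population". Sections 12.5.3, 12.6.4 and 12.7.1 repeat both sets for the main, secondary and exploratory summaries, and 12.3.3 defines the Randomized Population.

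SAP 4.1 keeps only the PK population for these endpoints. SAP section 11 declares the change: "They will be analyzed only in the PK population. The randomized population will not be defined". It gives no reason.

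Under SAP 4.1.3 a randomized subject enters the PK population if at least one nicotine PK parameter can be derived and no major deviation affects evaluability of the main objective. SAP 4.2.1.1 settles that impact in advance only for certain eligibility criteria (inclusion 1, 2, 3, 4 and 7; exclusion 2 and 15). For the rest: "Other major protocol deviations will be assessed for their impact on the evaluability of the primary objective during the pre-analysis data review meeting". The categories in its Table 1 are not exhaustive. The product-misuse row ends with "Product use not compliant with planned regimen". Protocol 6.4 makes the study open-label: "the PMP and CRO personnel will be unblinded to the subject's sequence and product use".

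On listings, Protocol 12.1.3 says: "All data will be presented in listings, ordered by subject, study visit, product, and time point, unless otherwise specified". The SAP titles nearly all outcome listings for the PK population.

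**The concern.** The PK population is a per-protocol set: membership is decided after randomization, partly by judgement, by people who know which product was used on which day. Exclusion applies to the subject, so a problem on one day can remove all three product days. The protocol's second analysis set was the natural check on whether this matters, and the SAP removes it.

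The pharmacodynamic and puffing endpoints are affected most plainly. ABOUT scores, VAS craving and liking, and puffing topography do not depend on background-corrected nicotine, yet they are summarised only for subjects whose PK is evaluable. Protocol 2.2 asks whether the product is acceptable in both nicotine delivery and satisfaction, so these data bear directly on the study's purpose.

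**Working it through.** **Plan's own figure.** The plan gives no expected number of exclusions and no bias figure. The one figure built on the inputs used below is the C_max precision of 0.55 in Protocol 12.2. Simulating the three-period, six-sequence design from those inputs gives a 90th-percentile 95% CI width of about 0.31, so 0.55 is not reproduced, although 0.55 or less is met. That is a separate matter. With 30 or 24 evaluable subjects the width would be about 0.35 or 0.40, so the issue here is selection and not lost precision.

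**Do other analyses cover the exclusions?** SAP 6.5.2 has two sensitivity analyses. One drops study days whose baseline nicotine exceeds 5% of the maximum. The other substitutes values when background correction fails in 2 or more subjects in a sequence. Neither puts back subjects excluded for deviations.

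**Listings by population (SAP 13.3).**
- Concentration and PK parameters: 10 (15.3.3.1.1 to 15.3.3.1.10), all PK population.
- ABOUT and VAS: 4 (15.3.5.1.1 to 15.3.5.1.4), all PK population.
- Puffing: 3 (15.3.5.2.1 to 15.3.5.2.3), all PK population.
- Cartridge weight and nicotine delivered: 1 (15.3.2.5), Safety population.

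That is 10 + 4 + 3 = 17 of 18 (94%) limited to the PK population.

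**Size of a possible shift.** Inputs from Protocol 12.2.1: geometric means 11 and 12 ng/mL (ratio 0.917), geometric CV 80%, within-subject log correlation 0.8; n = 36.
- Log variance: ln(1 + 0.8²) = 0.495; SD σ = 0.703.
- Standard error of a variant-minus-cigarette log difference: √(2 × (1 − 0.8) × 0.495 / 36) = 0.074.
- If k subjects are removed because of low C_max on one product, and m is their mean distance below that product's mean log C_max, the expected shift is (1 − 0.8) × k × m / (36 − k).

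Both k and the selection rule are assumptions. In 20,000 simulated trials m is 0.87 for random draws from the lowest 9 subjects. For the k lowest it is 1.489, 1.342, 1.237 and 1.153 (k = 1 to 4).

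| k | random from lowest 9 | the k lowest |
|---|---|---|
| 1 | 0.2 × 1 × 0.87 / 35 = 0.005 | 0.2 × 1 × 1.489 / 35 = 0.009 |
| 2 | 0.2 × 2 × 0.87 / 34 = 0.010 | 0.2 × 2 × 1.342 / 34 = 0.016 |
| 3 | 0.2 × 3 × 0.87 / 33 = 0.016 | 0.2 × 3 × 1.237 / 33 = 0.022 |
| 4 | 0.2 × 4 × 0.87 / 32 = 0.022 | 0.2 × 4 × 1.153 / 32 = 0.029 |

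The simulated shifts agree to within about 0.001. The sign depends on which product drives exclusion: positive if low uptake on the variant does, negative if low uptake on cigarettes does, and about zero if low uptake overall does. At the largest value the ratio moves from 0.917 to 0.943 (0.917 × e^0.029) or to 0.891 (0.917 × e^−0.029).

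**The case against.** A reader might infer that the SAP removes smokers who take few puffs or stop early with a variant, moving its ratio to cigarettes toward 1 and raising mean liking. The documents do not support that. Use is ad libitum, and Protocol 6.2 leaves subjects free to stop, so taking few puffs complies with the regimen. Stopping before the 6-minute window might be called non-compliant, but it excludes a subject only if judged to affect evaluability, and no section says it would. The Table 1 row mainly concerns other nicotine products and washout breaches.

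A reader might also infer that reviewers act on the results. Nothing says that nicotine concentrations are seen at the review meeting. SAP 4.2.1 has deviations categorised before database lock, and the SAP itself is to be final before lock.

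A third inference is that excluded subjects' data cannot be checked. That goes too far. Nicotine delivered, product-use times, sampling times and deviations are listed for the Safety population. Deviations are also tabulated by evaluability impact. SAP section 10 plans to list all CRF data by subject, and the report appendices include CRFs of randomized subjects and the bioanalytical reports. Shells and titles may change without an SAP amendment.

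The change is openly declared, the entry rule is permissive, the two sets may coincide, and the study tests no hypothesis. All of this limits the severity. It does not supply a reason for the deletion or an analysis that shows the effect of exclusions. No listing titled for a wider population shows an excluded subject's concentrations or PK parameters.

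**Conclusion.** The point holds as an unexplained departure from the protocol that removes the only planned check on exclusions from the PK population. It is a cheap improvement and not a demonstrated bias.

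Direction and size cannot be known from the documents. Under the Protocol 12.2.1 inputs, with an assumed 1 to 4 exclusions driven by low C_max on one product, the log ratio shifts by about 0.005 to 0.03 toward or away from P4M3, below the standard error of about 0.074. Exclusions picked directly on a low variant-to-cigarette ratio would move it more: about 0.027 for one subject and 0.050 for two. Nothing in the plan suggests such a rule. No figure can be given for liking or the other subjective scores, because the documents state no variability for them.

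**What to change.** Reinstate the Randomized Population as Protocol 12.3.3 defines it, and keep the PK population for the main ANOVA. If the two populations differ by at least 1 subject, the trigger that Protocol 12.4 already uses for demographics, then:
- repeat the ANOVA on the randomized population, using every product day with a derivable parameter;
- summarise ABOUT, VAS craving and liking, puffing topography and nicotine delivered on the randomized population.

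Retitle Listings 15.3.3.1.1 to 15.3.3.1.10, 15.3.5.1.1 to 15.3.5.1.4 and 15.3.5.2.1 to 15.3.5.2.3 to the Randomized Population, with a flag for exclusion from the PK population.

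The cost is SAP wording, listing titles with one added flag and, when a randomized subject is excluded, one rerun of existing programs. No new data, subjects or procedures are needed. The downside is a second set of tables to report in that case.
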